- Submission of knowingly false information from the research facility to the Sponsor, study monitor, or appropriate regulatory authority.

Subjects who withdraw from the study for any reason will not be replaced. Subjects who voluntarily withdraw from the study will be asked to complete the Week 6/Early Termination assessments. Subjects who are withdrawn due to adverse events will be followed until resolution or stabilization of the adverse event.

SAMPLE SIZE

The primary endpoint of the study is clinical response at Week 6, defined by 50% or greater reduction on the Hamilton Rating Scale for Depression (HAM-D¹⁷) from baseline (Day 0). The null and alternative hypotheses of interest are:

$$H_0: \pi_A - \pi_S = 0$$

vs.

$$H_a: \pi_A - \pi_S \neq 0$$

where π_A is the proportion of subjects who show 50% or greater improvement in HAM-D¹⁷ total score from baseline (Day 0) to Week 6 for the active sTMS treatment and π_S is the equivalent value for the sham-controlled group.

The calculation of sample size requirements for this confirmatory study is based on the results observed in the per-protocol (PP) analysis of non-treatment-naïve subjects who completed Week

6 HAM-D¹⁷ assessments in the previous NEST trial NND-3001.

In that population, 34% of subjects treated with active sTMS were categorized as responders, whereas only 8% of sham treated subjects responded. Assuming true population response rates of 34% for sTMS and 8% for Sham, power analysis indicates that a PP sample size of 92 subjects (i.e., 92 subjects, or 46 subjects per treatment group, without major protocol violations and with HAM-D¹⁷ measured at Week 6) yields 81% power to demonstrate superiority of sTMS over Sham, where the statistical test is Fisher's exact test at a two-sided 0.05 level of significance.

The sample size ratio for the active treatment group to sham-controlled group is 1:1. Based on a conservative estimate of published studies, approximately 23% of enrolled subjects may not be part of the PP population in each treatment group. Thus, a total of 120 subjects (60 per group) will therefore be enrolled in the study to account for potential drop-outs and protocol noncompliance prior to Week 6.

SCHEDULE OF VISITS

Table A on the following page displays the schedule of visits and procedures for protocol NND-3002. Full details can be found in the protocol.

TABLE A: STUDY FLOWCHART

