The primary hypothesis in the double-blind phase will be tested using Fisher's Exact test on the ITT and PP analysis populations. For the ITT population, there may be missing data at Week 6 due to, for example, patients prematurely withdrawing from the study. The first analyses for the ITT population will use available data. As a supportive sensitivity analysis, multiple imputation will be used to assess the robustness of the primary endpoint findings relative to missing data. Specifically, multiple imputation using the linear regression approach will be used to impute missing HAM-D¹⁷ across visits via SAS PROC MI; included as covariates in the linear model will be age, sex, race, education level, HAM-D17 measured at previous visits, investigative center, baseline MMSE, baseline IDS-SR, baseline C-SSRS, and ATHQ categorizations. Ten complete datasets will be created (the linear regression approach to multiple imputation assumes monotone missing data pattern; if such a pattern does not exist, then prior to each of the 10 linear regression imputations, any non-monotone missing data will first be imputed via the Monte-Carlo Markov Chain approach to create a monotone missing data pattern). Once 10 complete HAM-D¹⁷ datasets are generated, the determination of whether the patient achieved imputed clinical response at Week 6 will be calculated for each patient with missing data within each imputed dataset. The z-test for proportions with continuity correction (which yields very similar results to Fisher's Exact test) will then be applied to each of these 10 datasets to compare treatments on

the incidence of Week 6 clinical response. The numerator and denominator of the 10 continuity-corrected z -statistics will then be combined into a single continuity-corrected z-statistic using SAS PROC MIANALYZE. The resulting p-value from this z-statistic, assessing overall significance of treatment difference on clinical response rate at Week 6, will be calculated.

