The following secondary measures are to be considered for labeling. They will be analyzed using the gatekeeper (sequential) strategy to control for multiple comparisons by pre-specifying the order of testing (Westfall and Krishen, 2001). If the primary analysis is significant, these outcomes will be tested in the order listed below, each at the 0.05 alpha level. Testing for label consideration will cease when the first outcome results in a two-sided p-value greater than 0.05.

- Change from Baseline on the HAM-D¹⁷ score at Week 6;
- Change from Baseline on the MADRS score at Week 6;
- Clinical response, defined by 50% or greater reduction on the MADRS total symptom score at Week 6.

Treatments will be compared on the mean change from baseline HAM-D¹⁷ and MADRS scores at Week 6 using analysis of covariance adjusting for the baseline value of the given endpoint. Treatment group comparisons on the proportion of subjects who achieve MADRS clinical response at Week 6 will be carried out using Fisher's Exact test. Tests of hypotheses will be two-sided.

Assessment of investigator center-by-treatment interaction will be carried out using Breslow-Day test for the MADRS clinical response at Week 6 and using analysis of covariance with the independent variables of treatment group, investigative center, and the treatment-by-investigative interaction for change from baseline in HAM-D¹⁷ and MADRS at Week 6. Again, a non-significant interaction (using a 0.15 level of significance) or a significant interaction deemed only quantitative in nature supports the pooling of results across centers for the analyses on these secondary endpoints.

Multiple imputation for the ITT population for each endpoint will be carried out using linear regression in a similar manner as for the primary endpoint. For MADRS clinical response, the overall significance of the difference between treatment groups across the imputed datasets will be carried out in the same manner as for the primary efficacy endpoint. For the mean change from baseline at Week 6 for each of HAM-D¹⁷ and MADRS, analysis of covariance comparing treatments adjusting for the baseline value of the endpoint will be carried on each imputed dataset with the results being combined across imputed datasets using PROC MIANALYZE to obtain one overall assessment of treatment difference on the mean endpoint, adjusting for baseline.

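### Ten imputations leave avoidable Monte Carlo noise in the supportive ITT multiple-imputation analysis when its p-value falls near 0.05; at least 100 would remove most of it at no real cost

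*SAP*

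**What the plan says.** SAP section F (sensitivity analyses on the primary endpoint) first tests ITT response on available data and then adds multiple imputation. The role is explicit: "As a supportive sensitivity analysis, multiple imputation will be used to assess the robustness of the primary endpoint findings relative to missing data". Missing HAM-D17 scores are imputed across visits by linear regression in PROC MI, with an MCMC step first if the missingness is not monotone. The number is fixed: "Ten complete datasets will be created". "The z-test for proportions with continuity correction" is then applied to each completed dataset, and PROC MIANALYZE combines the results into one z-statistic and one p-value for the treatment difference.

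The SAP states no random seed, no Monte Carlo error target and no rule for adding imputations.

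The approach is reused. Section G repeats the subgroup analyses on imputed ITT data. Section H, on secondary endpoints for labelling, says: "Multiple imputation for the ITT population for each endpoint will be carried out using linear regression in a similar manner" as for the primary endpoint.

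The primary test does not depend on any of this. It is Fisher's exact test on the per-protocol (PP) population "at a two-sided 0.05 level of significance". A missing Week 6 HAM-D17 excludes a subject from PP, and Protocol section 11.5 says that PP therefore has no missing primary endpoint data.

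**The concern.** A pooled multiple-imputation p-value is itself an estimate. With few imputations it moves from seed to seed on identical data. The SAP ends the procedure in a single p-value for significance, so a borderline result could land on either side of 0.05 by the draw of random numbers.

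The question it addresses matters in this trial. The primary population is PP, and Protocol section 1.1 shows that populations can disagree. In the previous trial's non-naive subjects, HAM-D17 response gave p = 0.17 in ITT and p = 0.01 in completers. A reader will want to know whether a PP result holds among all randomised subjects, and the imputation analysis is one of the checks on that. Noise that a larger number in one sentence would remove should not blur it.

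**Working it through.** **Plan figures.** The plan gives no Monte Carlo error, so there is no figure of that kind to reproduce. The sample-size figures that set the scale of the simulations do reproduce.

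- Inputs (SAP, Sample Size): "Assuming true population response rates of 34% for sTMS and 8% for Sham"; "92 subjects, or 46 subjects per treatment group"; "yields 81% power to demonstrate superiority of sTMS over Sham".
- The continuity-corrected formula, an approximation to Fisher's test, gives an effective n of 46 × (1 − 1/(46 × 0.26))² = 38.6 per arm and power of 81.4%.
- 92/(1 − 0.23) = 119.5, which rounds to 120 enrolled.

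**Assumption.** The documents give neither the expected share of missing Week 6 HAM-D17 nor the fraction of missing information *f*. I take *f* = 5%, 10% and 20%.

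**Formula.** Scale the total variance to 1, so that the between-imputation variance is *f* and the within-imputation variance is 1 − *f*. With *m* imputations, estimated between-imputation variance B and mean estimate Q̄, Rubin's rules give

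T = (1 − *f*) + (1 + 1/*m*)B and z = Q̄/√T.

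Around a limiting z of 1.96, the seed-to-seed variance is approximately

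Var(z) ≈ *f*/*m* + [(1.96/2)(1 + 1/*m*) *f* √(2/(*m* − 1))]².

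- *f* = 5%, *m* = 10: 0.0050 + 0.0254² = 0.0056, SD 0.075
- *f* = 10%, *m* = 10: 0.0100 + 0.0508² = 0.0126, SD 0.112
- *f* = 20%, *m* = 10: 0.0200 + 0.1016² = 0.0303, SD 0.174

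**Simulation of the same pooling.** With 20,000 seeds and a limiting two-sided p of 0.05, the reported p (5th to 95th percentile, normal reference) was:

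| *f* | *m* = 10 | *m* = 100 |
|---|---|---|
| 5% | 0.038–0.067 | 0.046–0.055 |
| 10% | 0.033–0.077 | 0.044–0.057 |
| 20% | 0.026–0.095 | 0.041–0.061 |

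Using Rubin's t degrees of freedom changes these little.

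**Check by actual re-imputation.** Weekly HAM-D17 scores were simulated at 60 per arm with monotone dropout. They were imputed by sequential regression on baseline and previous visits (fewer covariates than the SAP lists), tested with the continuity-corrected z and pooled. The table covers seven or eight datasets per row with a large-*m* p between 0.04 and 0.06. The last column is the share of seeds that put the *m* = 10 result on the other side of 0.05 from the large-*m* result.

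| Missing Week 6 (assumed) | SD of p, *m* = 10 | SD of p, *m* = 100 | Other side of 0.05, *m* = 10 |
|---|---|---|---|
| 5% | 0.006 | 0.002 | 23% |
| 10% | 0.008 | 0.0025 | 24% |
| 23% | 0.017 | 0.005 | 39% |
| 33% | 0.022 | 0.006 | 41% |

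In six individual datasets from this model at 23% missing, *f* ran from about 0.11 to 0.19, so the assumed range is a reasonable one. The 23% is the SAP's allowance for subjects outside PP. The 33% is the previous trial's non-completers, (202 − 135)/202. Both also count noncompliance, so they are proxies only.

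**Sample-size increase.** A larger trial does not remove the noise. In a simpler model that draws missing responses directly, 120 per arm with 23% missing gave a mean p of 0.059 and a 95% range over seeds of 0.019 to 0.125 at *m* = 10.

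**Away from 0.05.** With a limiting p of about 0.021 and *m* = 10, the call changes in under 0.5% of seeds at *f* = 10% and about 3% to 4% at *f* = 20%. At about 0.012 it is under 0.5% in both.

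**The case against.** The strongest reply is that little depends on this analysis. Several parts of it stand.

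- The primary PP test has no missing data, and the SAP calls the imputation analysis supportive.
- Section F also contains the available-data ITT test and a tipping-point analysis that steps through assumed outcomes for the missing subjects. Neither needs a seed. The question of whether a PP result carries over to the randomised groups does not rest on imputation alone.
- Rubin's rules include the 1/*m* term. Ten imputations introduce no bias and leave no variance uncounted. The issue is reproducibility, not validity.
- *f* is assumed, and 23% is a weak anchor for it. Noncompliant subjects may still have a Week 6 score, Protocol section 8.2 asks sites to collect HAM-D from those who discontinue, and earlier HAM-D17 scores in the imputation model can lower *f*. Even so, at 5% the range still straddles 0.05.
- No result near 0.05 is predicted. It is possible: the previous trial's non-naive ITT rates were 27% and 15%, the 12-point difference to which the 240-subject cap is tied. At 120 per arm these give a continuity-corrected z of about 2.12 (p about 0.034) with complete data. Losing 10% to 20% of the information gives p of about 0.044 to 0.058. That is one scenario, not a forecast.

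A reader might infer that the seed could decide the trial, a label claim or a subgroup finding. The documents do not support that. The section H sequence opens on the primary analysis, for which the SAP names PP as the population, and no rule makes the imputed ITT result the gate. Section G says that the subgroup analyses assess consistency, not significance. Nor does the SAP's silence on a seed show that none would be fixed, since it may be set in the analysis program.

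**Conclusion.** The point holds as a conditional one. If the pooled ITT p-value falls near 0.05, ten imputations leave noise that can change how it reads: an SD in z of about 0.07 to 0.17 for an assumed *f* of 5% to 20%. One hundred imputations cut that SD by a factor of about three (√10 ≈ 3.2). They do not remove it: a result almost exactly at 0.05 can still fall either way.

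The mechanism is certain. The size rests on the assumed fraction of missing information, and the conclusion is the same across the range tried. The consequence is confined to the imputed ITT results in sections F, G and H. The primary result, the sample size, the PP secondary tests, the available-data analysis and the tipping-point analysis do not change. This is a free improvement of low severity, not an error in the plan.

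**What to change.** In SAP section F, replace ten completed datasets with at least 100, and state that the same number applies to the imputed analyses in sections G and H. In the regression-imputation check, 100 kept the seed-to-seed SD of p at or below 0.005 for up to 23% missing, against 0.017 with ten.

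Record the random seed before unblinding as well. That makes the reported figure reproducible and removes any choice of seed after the fact, but it does not reduce Monte Carlo error. Only the larger number of imputations does that.

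The cost is a line of SAP text and trivial computing time. No subject, visit or data collection is affected, and there is no statistical downside.

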5.7 PRIOR AND CONCOMITANT MEDICATION

Prior medications are defined as all medications taken within 30 days (whether continuing or not) prior to post-washout screening/baseline (Day ≤ 0). All prior and concomitant medications must be listed in the subject's medical record and recorded on the CRF. Subjects should be questioned at each study visit concerning any new medications or changes in current medications.

For each medication taken, the following information will be collected:

- Medication trade name.
- Indication for which the medication was given.
- Dose, route, and frequency of administration.
- Date started.
- Date stopped.

Subjects will be instructed not to begin any new medication before consulting with the Investigator (unless required for emergency medical use). The subject will be instructed that this prohibition applies to over-the-counter and herbal products as well as prescription drugs.

All subjects will be tapered off their existing antidepressant medications during Screening (if applicable) and may receive only permitted concomitant medication as deemed necessary by the Investigator. All antidepressant medications must be discontinued for 1 week (7 days) prior to post-washout Baseline assessments (Day 0). Concomitant medications should be kept to a minimum during the study. The Investigators are recommended to use these medications in accordance with usual clinical practice and only medications essential for the subject's well-being should be used. If such medication is deemed essential, subjects should stay on their usual medication regimens at stable doses during the entire course of the study.

If necessary, benzodiazepines ($\leq 0.5\text{mg}/2\times\text{week}$ lorazepam or equivalent dose of benzodiazepine) may be used for agitation/anxiety. For sleep, partial benzodiazepine agonists, including zolpidem 5 to 10 mg/day, zaleplon 5 to 10 mg/day, and eszopiclone 2-3 mg/day, may be used on an exceptional basis for insomnia/sleep disturbance within the prescribing doses for insomnia. Any equivalent short half-life non-benzodiazepine hypnotic may be substituted if zolpidem, zaleplon, or eszopiclone are not available (i.e. chloral hydrate). These drugs should not be used for 72 hours prior to the initial evaluation visits.

Questions regarding the use of concomitant medications should be addressed to the study Monitor.

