In addition, a tipping point analysis will be performed to assess the likelihood that the observed significance would no longer hold based on various assumed values of the missing clinical response data. Specifically, to start, at Week 6, all missing data will be assumed to be successes for both the sTMS and sham groups. Fisher's exact test will then be run comparing treatments on this imputed clinical response rate and the treatment comparison Week 6 p-value will be generated. Then, the analyses will be repeated where 1 missing sTMS patient is assumed to be a failure, and all remaining sTMS and all Sham patients are assumed to be successes. Then the analyses will be repeated where 2 missing sTMS patients are assumed to be a failure, and all remaining sTMS and all Sham patients are assumed to be successes. This process will continue until the "tipping point" is reached. The "tipping point" is the imputation point at which the Fisher's Exact test p-value changes from significance to non-significance.

The above process will then be repeated but where 1 missing Sham patient is assumed to be a failure throughout the above one-failure-at-a-time imputation for sTMS patients. It will then be repeated but where 2 missing Sham patients are assumed to be a failure throughout the imputations for sTMS patients, etc.

G. Subgroup Analyses

The robustness of the primary efficacy outcome will be confirmed via subgroup analyses. Subgroups of subjects will be identified according to their investigative center, gender, age (<median, ≥median), education, concomitant medication, ATHQ history and duration of illness (<median, ≥median). The Fisher's Exact test on the primary endpoint analysis will be repeated within the subgroups of subjects defined by levels of the variable (e.g. adults < median age, adults ≥ median age). The purpose of this subgroup analysis is not to find significant treatment effect within subgroups, but rather to assess consistency of treatment effect across subgroups. This will be performed on the ITT population with available data and imputed data, and on the PP analysis population.

H. Secondary Analyses for Label Considerations

The following analyses will be conducted for the ITT (available and imputed data) and PP populations.

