A urine toxicology dipstick screen will be performed at screening visit in order to rule out use of unprescribed psychoactive medications. All subjects with a positive test must be withdrawn from the study unless a subsequent negative test is obtained (this may only occur once prior to randomization). These subjects will be informed that urine samples may be obtained on additional occasions during the study, but will not be told how many samples nor about the time at which the samples will be collected. Sites may conduct an optional urine toxicology screen if the Investigator feels it is indicated at any time during a subject's study participation. Urine Toxicology Screening will be provided in data listings.

K. Other Assessments

1. Concomitant Medications are collected at Baseline and throughout the study through Week 12. All medications prescribed and/or taken by the subject will be collected. Any changes to these medications may be updated at any visit. Concomitant medications will be provided in data listings.

2. Verification of Blinding Questionnaire:

A treatment blinding questionnaire will be administered to treatment administrator ("treaters"), raters and patients at Treatment Day 5 (end of Week 1) and Treatment Day 30 (end of Week 6, or i.e. end of the double-blind phase). This brief questionnaire will ask participants to (a) provide a best guess of the treatment to which the patient was randomized (sTMS or Sham), (b) a reason for the guess (improvement or lack thereof; how the machine operated; something the subject, rater, or treatment administrator did or said; no reason); and (c) confidence level of the guess (Extremely; Considerably; Moderately; Slightly; Not at All).

From the "best guess" and its "confidence level", a blinding index will be calculated at each of Treatment Days 5 and 30, similar to the blinding index discussed in Bang et al. (2004)¹ and Kolahi et al. (2009)². Specifically, for each treater, rater, and patient at each visit, a blinding index will be created as follows:

- If a treater/rater/patient correctly guessed the patient's randomized treatment group AND was extremely or considerably confident in the guess, then **the blinding index will be set to 1** for that treater/rater/patient

¹ Bang H, Ni L, Davis C E. Assessment of blinding in clinical trials. *Controlled Clinical Trials*. 2004; 25: 143-156.

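### SAP section G aims to show a consistent effect across subgroups but specifies only separate Fisher tests within levels, and it sets no time window for the concomitant-medication subgroup

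*SAP*

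**What the plan says.** SAP section G (Subgroup Analyses) opens with "The robustness of the primary efficacy outcome will be confirmed via subgroup analyses". It lists seven variables: centre, gender and age, followed by "education, concomitant medication, ATHQ history and duration of illness". The Fisher's exact test of the primary endpoint "will be repeated within the subgroups of subjects defined by levels of the variable", on the ITT population (available and imputed data) and on the PP population. The stated purpose is "not to find significant treatment effect within subgroups, but rather to assess consistency of treatment effect across subgroups".

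Section G names no subgroup effect estimate, confidence interval, interaction test or rule for reading the results. The SAP has suitable tools elsewhere. Under Analysis of Primary Efficacy Endpoint it specifies a Newcombe (Wilson-type) 95% interval for the overall risk difference. It also specifies a Breslow-Day test of treatment by centre at the 0.15 level, after pooling sites with fewer than 10 PP subjects.

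On medication, SAP section K says "Concomitant Medications are collected at Baseline and throughout the study through Week 12". Protocol section 5.7 has a separate term for earlier use: "Prior medications are defined as all medications taken within 30 days (whether continuing or not) prior to post-washout screening/baseline". Section G does not say which period defines its concomitant-medication subgroup.

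**The concern.** A Fisher test within one level asks whether there is evidence of an effect in that level. Section G says this is not its question. Whether two levels differ in effect is a separate question, and a pair of p-values does not answer it: the larger level can be significant and the smaller not, with the same effect in both. Given only these tests, a reader could take a mixed pattern as lack of robustness, or could pick out the significant levels as support.

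The medication subgroup raises a second issue. Protocol section 5.7 allows limited benzodiazepine and hypnotic use on study, and SAP section I treats anxiety and sleep as HAM-D17 subscales. If the subgroup were defined by on-study use, membership could depend on how a subject responds to treatment. The comparison within that subgroup would then lose the protection of randomisation.

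**Working it through.** **Inputs.** From SAP, Sample Size: "Assuming true population response rates of 34% for sTMS and 8% for Sham"; "Fisher's exact test at a two-sided 0.05 level of significance"; 92 evaluable subjects, 46 per arm, 1:1. From SAP, Interim Analyses: a maximum of about 184 evaluable. The documents do not give subgroup shares, so an even split is the base case and 60:40 to 80:20 is shown as a range. The two age levels and the two illness-duration levels are median splits, so an even split fits them.

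**1. The plan's own figure.** Continuity-corrected normal approximation at n = 46 per arm:

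- difference 0.34 − 0.08 = 0.26; mean rate 0.21
- null SE = √(2 × 0.21 × 0.79 / 46) = 0.0849
- alternative SE = √((0.34 × 0.66 + 0.08 × 0.92) / 46) = 0.0805
- power = Φ[(0.26 − 1/46 − 1.96 × 0.0849) / 0.0805] = Φ(0.892) = 81.4%

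This agrees with the stated 81%. Exact enumeration of Fisher's test gives 83.6%, so the stated figure is slightly conservative.

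**2. Power within one level.** With n per arm in the level, exact power is

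Σᵢ Σⱼ Bin(i; n, 0.34) × Bin(j; n, 0.08) × 1{Fisher p ≤ 0.05}.

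At n = 23 this is P = 0.4955.

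**3. Two equal halves with the same true effect.** The halves are independent, so:

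- both significant: P² = 0.4955² = 24.6%
- exactly one: 2P(1 − P) = 2 × 0.4955 × 0.5045 = 50.0%
- neither: (1 − P)² = 25.4%

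**4. Maximum size.** At 184 evaluable, each half has 46 per arm and P = 0.836. Both are significant in 69.9%, exactly one in 27.4% and neither in 2.7%.

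**5. Uneven splits (shares assumed).** Exactly one level significant, P₁(1 − P₂) + P₂(1 − P₁):

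| Split | 92 evaluable | 184 evaluable |
|---|---|---|
| 50:50 | 50% | 27% |
| 60:40 | 52% | 31% |
| 70:30 | 58% | 45% |
| 80:20 | 70% | 63% |

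**6. Several variables together.** In 8,000 simulated trials of 92 evaluable subjects, with five even two-level variables independent of each other and of outcome, at least one variable showed one significant and one non-significant level in about 85% of trials.

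**7. A smaller effect.** With 27% vs 15% (the non-naive ITT rates in Protocol section 1.1), P at 23 per arm is 0.105. Neither half is significant in 0.895² = 80%. The output is then uninformative rather than mixed.

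**8. An interaction test on the same data.** With an identical effect and 23 per arm per half, a Breslow-Day test flags a difference in 4.6% of simulated trials at 0.05 and 16.6% at 0.15. A z-test of the difference between the two risk differences flags 6% and 16%. In about 2% of trials (0.92⁴⁶ = 0.022) there are no sham responders at all; these were left out of the Breslow-Day figures.

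**9. Limit of that test.** If one half has the full effect (34% vs 8%) and the other none (8% vs 8%), the risk-difference interaction test at 0.05 detects it in about 49% of trials at 23 per arm per half.

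**The case against.** Section G disclaims a search for significance and nowhere equates consistency with p < 0.05 in every level. Someone comparing the direction of the response rates would see little trouble: with 34% vs 8% in both halves and 23 per arm, sTMS is ahead in both in about 97% of trials (0.983² = 0.966). The SAP's general methods call for frequencies and percentages for discrete variables, so response rates would probably appear beside the p-values. This stands in part. A misreading is a risk, not a certainty, but section G still specifies no effect measure or reading rule.

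Two stronger readings are tempting, and the documents do not support them.

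- **That the analysis would usually look inconsistent when the effect is the same.** Both halves are significant in only 25% of trials, but the other 75% is not all discordant: in a further 25% neither is significant. For one even split, discordance is 50% at 92 evaluable and 27% at 184. It exceeds half only for uneven splits or several variables taken together, and only if consistency is judged by comparing significance.
- **That the medication subgroup is defined by post-randomisation use.** The SAP leaves this open. A concomitant medication history is among the screening and baseline assessments, so a baseline definition is possible. Room for on-study change is also limited: Protocol section 5.7 asks for stable doses of essential medication, and prohibited medication removes a subject from the PP population. Permitted sedatives and hypnotics can still vary.

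Centre is already covered by the Breslow-Day test and the pooling rule, so the criticism does not extend to it.

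**Conclusion.** The point holds for the six non-centre variables. The specified method does not measure what section G sets out to assess. With the planning effect identical in two equal halves, one significant and one non-significant result would occur in about 50% of trials at 92 evaluable and about 27% at 184. The figures assume 34% vs 8% in every level and the subgroup shares shown. They describe what happens if levels are compared by significance, a reading that the SAP neither states nor replaces with another.

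The medication window is an omission to close, not a demonstrated bias. The subgroup analyses are supportive, so the primary test, its alpha and the sample size are untouched. This is a minor but free improvement.

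**What to change.** In SAP section G, before unblinding:

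1. For gender, age, education, concomitant medication, ATHQ history and duration of illness, report in each level the response rates by arm and the risk difference with the Newcombe 95% interval already used for the primary endpoint. A forest plot would show these well.
2. Add one treatment-by-subgroup interaction test per variable, for example Breslow-Day as for centre. State its level and what is done when a table has no sham responders. Say that it is supportive, that its power is limited, and that the estimates and intervals carry the interpretation.
3. Drop the within-level Fisher p-values, or state that they are not used to judge consistency.
4. Define the concomitant-medication subgroup by use at baseline and give the window, or label the subgroup post-randomisation and interpret it accordingly. The window matters because Protocol section 5.8 bars several permitted drug classes within 72 hours of the baseline EEG, so use on Day 0 alone would miss them. The 30-day window for prior medication in Protocol section 5.7 is one candidate.

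The cost is SAP wording and one standard output. No additional data are collected.
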